5. DURATION

The anticipated duration of the study is approximately 5 years. The duration for participants is variable depending on their level of adherence during the baseline period and their enrollment date as the follow-up period was shortened twice to continue enrollment and allow participants to complete the study by the end of the grant period.

- For enrolled participants who achieve electronically monitored adherence >95% in the baseline period, their study participation will be approximately 2 months, with conclusion at the end of the baseline period.
- For participants with adherence < 95% in the baseline period, their participation will be:
 - 20 months (2 months baseline, 5 months of active intervention, and 13 months of follow-up) if they enrolled before 12/9/2022.
 - 14 Months (2 months baseline, 5 months of active intervention, and 7 months of follow-up) if they enrolled between 12/9/2022 and 3/8/2023.
 - 8 months (2 months baseline, 5 months of active intervention, and 1 month of follow-up) if they enroll after 3/8/2023.

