After completion of Stage 2, automated digital reminders will be turned off and adherence feedback reports will cease to be provided. Additional questionnaires will be completed via REDCap at Post-Treatment (1-Month Follow-Up in Month 8), Follow-Up 1 (6 months post-treatment in Month 14)*, and Follow-Up 2 (12 months post-treatment in Month 20)**.

Data collection procedures and measures: Participants will complete a demographic questionnaire that provides general information about the child's age, caregiver work history, family composition, socio-economic status, family history of seizures, history of seizures (e.g., type, who witness, when they occurred), and comorbid illnesses (e.g., learning disorders). In addition, caregivers will complete the questionnaires detailed in the table below.

Construct Measured	Respondent C=Caregiver; M=Medical Chart Review D=Doctor/Clinician	Stages and Time points			
		Baseline	Post (1 month post- treatment)	Follow-Up 1 (6 months post- treatment) *	Follow-Up 2 (12 months post- treatment) **
ORDER OF MEASURES (As applicable)					
Background Form (Demographic)	C	X			
Pediatric Epilepsy Medication Self-Management Questionnaire (PEMSQ) 
 PEMSQ: Self-reported Adherence 	C	X	X	X	X
Behavior Assessment System for Children-3 Parent-Rating Scales	C	X	X	X	X
Short Test of Functional Health Literacy in Adults	C	X	X	X	X
Pediatric Quality of Life in Epilepsy Module	C	X	X	X	X
Brief Symptom Inventory-18 (BSI-18)	C	X	X	X	X
Epilepsy Knowledge Questionnaire-Adapted (EKQ)	C	X	X	X	X

Social Problem-Solving Inventory-Revised Short (SPSI-Revised Short)	C	X	X	X	X
Pediatric Epilepsy Side Effects Questionnaire (PESQ)	C	X	X	X	X
Seizure Severity Scale Adapted for Children (SSSC)	C	X	X	X	X
Family Assessment Device (FAD)	C	X	X	X	X
Global Assessment of the Severity Scale of Epilepsy in Children (GASE)	D	X	X	X	X
Healthcare utilization	C	X	X	X	X
Medical Chart Review	M	X	X	X	X
Feasibility/Acceptability Questionnaire (FAQ)	C		X		
Impact of COVID-19 on Pediatric Epilepsy Management (ICPEM)	C	X	X	X	X

*Follow-Up 1 Questionnaires will only be completed by participants enrolled before 3/8/2023

**Follow-Up 2 Questionnaires will only be completed by participants enrolled before 12/9/2022

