Secondary analyses will compare the mean outcomes associated with each of intervention strategies #1 - #3 embedded in the SMART on the basis of the outcomes adherence, seizure severity/frequency, HRQOL, and healthcare utilization at 1-, 6-, and 12-months post-intervention. Strategies #1 and #2 are non-adaptive intervention strategies in that intervention is not modified in accordance with Stage 1 adherence status (or any other participant characteristics), while #3 is an adaptive intervention strategy in that intervention is augmented by problem-solving in Stage 2 only under non-adherence in Stage 1. The pairwise comparison of the non-adaptive strategy #1 to the adaptive strategy #3 represents comparison of the least resource-intensive strategy (control) to the most resource-intensive strategy. Comparison of strategies #1, #2, and #3 will be carried out using specialized methods for SMART analysis based on inverse probability weighting for estimation of the mean outcome associated with a strategy that account for the fact that actual experiences of participants may be consistent with more than one strategy; for example, a participant who is randomized to intervention in Stage 1, is adherent in Stage 1 (i.e., is a responder to intervention), and continues to receive intervention in Stage 2 is consistent with having followed either embedded strategy #2 or #3. In this case, a participant's data contributes to assessment of improvement in outcome for both strategies. For each strategy, the inverse probability weighting is by the reciprocal of the estimated probability that a participant's experience is consistent with the strategy. We will conduct pairwise comparisons of the three embedded strategies using these methods based on adherence, seizure severity/frequency, HRQOL, and healthcare utilization at 1, 6-, and 12-months post-intervention. We will also conduct a global test of the null hypothesis that the mean outcomes associated with the three strategies are the same versus the alternative that at least one mean differs from the others.

Exploratory Analysis Plan:

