For the secondary analyses, Stage 2 and later outcomes will be assumed to be missing according to a MAR mechanism. If the extent of missingness is less than 10% for each strategy, we will conduct complete case analyses comparing the embedded intervention strategies. To assess sensitivity of these analyses to missingness and to obtain a definitive analysis if the extent of missingness is greater than 10%, under the MAR assumption, we will use inverse probability weighting of complete cases in estimation of the mean outcomes associated with each strategy, where the outcomes are weighted by the reciprocal of the estimated probability not dropping out of the study/having the outcome observed as a function of baseline and previously observed variables based on logistic regression.

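### At 6 and 12 months, families whose follow-up was cut short inform the strategy means only through the weight model; a short augmented estimator would be a cheap gain in precision and robustness.

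*SAP*

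**What the plan says.** The SAP (Handling of Missing Data, secondary analyses) assumes that Stage 2 and later outcomes are missing at random. "If the extent of missingness is less than 10% for each strategy, we will conduct complete case analyses" comparing the embedded strategies. Above that level the definitive analysis is weighted: "we will use inverse probability weighting of complete cases in estimation of the mean outcomes associated with each strategy". The probability of being observed is modelled "as a function of baseline and previously observed variables based on logistic regression". The Secondary Analysis Plan adds a strategy weight, the "reciprocal of the estimated probability that a participant's experience is consistent with the strategy". No augmentation term, imputation or joint longitudinal model is mentioned. Nor does the SAP say whether the observation model is one pooled fit or is fitted by strategy or by treatment path.

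Protocol section 5 records that "the follow-up period was shortened twice to continue enrollment" and let families finish within the grant period. The latest group stays for "8 months (2 months baseline, 5 months of active intervention, and 1 month of follow-up) if they enroll after 3/8/2023". The footnotes to the measures table in section 8 give the consequence: "Follow-Up 1 Questionnaires will only be completed by participants enrolled before 3/8/2023", and "Follow-Up 2 Questionnaires will only be completed by participants enrolled before 12/9/2022". The SAP does not mention these cut-offs.

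**The concern.** Aim 2 compares the three strategies pairwise at 1, 6 and 12 months. Because of the cut-offs, the 6- and 12-month comparisons rest on the least data in the trial, and the sample size allowed for 10% attrition in each Stage 1 arm but nothing for shortened follow-up. A family seen at 1 month but never scheduled for the later visit has information about its likely later outcome. Weighted complete cases use that information only indirectly, through the fitted probabilities. How much precision this recovers for a difference between strategies depends on a modelling detail that the SAP leaves open. The planned estimator also relies wholly on the observation model being right.

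**Working it through.** **Inputs from the documents.** 180 intervention and 90 control at the end of Stage 1, 50% Stage 1 response, Bonferroni adjustment (SAP, Power and Sample Size Estimation).

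**Assumed, because the documents do not give them.** 1:1 second randomization, which puts 180 x 0.5 / 2 = 45 in each re-randomized path; a later visit unobserved at random in 20-60% of families; correlation between visits of 0.3-0.7.

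**The plan's own figures (normal approximation).**
- d = 0.36: 0.36 / sqrt(1/180 + 1/90) = 2.79, and 2.79 - 1.96 = 0.83, so power is 79.6% (stated 80%).
- d = 0.50: 3.87 - 1.96 = 1.91, so power is 97.2% (stated 97%).
- d = 0.69, 45 against 45, alpha 0.05/3: 3.27 - 2.39 = 0.88, so power is 81.0%, or 79.5% with the t distribution (stated 80%).

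These reproduce. The documents give no variance figure for the 6- or 12-month contrasts.

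**The two estimators.** For each family let V be the strategy weight, O = 1 if the later outcome Y is observed, p the fitted probability of observation, and m the prediction of Y from treatment path, baseline value, Stage 1 adherence and latest earlier follow-up value.
- Planned: sum(V O Y / p) / sum(V O / p). A family with O = 0 adds nothing to either sum; it acts only through the fit of p.
- Augmented: sum(V [m + O (Y - m) / p]) / sum(V). A family with O = 0 contributes its m.

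**Closed-form guide.** For one mean with outcomes missing completely at random, the variance reduction over constant weights is about (share unobserved) x R-squared.
- With one predictor: 0.2 x 0.3² = 1.8%; 0.4 x 0.5² = 10.0%; 0.6 x 0.7² = 29.4%.
- With three equally correlated predictors, R-squared = 3r² / (1 + 2r). At r = 0.7 this is 1.47 / 2.4 = 0.6125, and 0.6 x 0.6125 = 36.8%.

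**Simulation of this SMART (1,500 trials per cell).** The augmented estimator used path intercepts and common slopes. Ranges run over the three pairwise contrasts and all assumed shares and correlations.

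| How the planned observation model is fitted | Variance, augmented / planned | Reduction |
|---|---|---|
| One pooled model, no path terms | 0.62-0.98 | 2-38% |
| One pooled model with path indicators | 0.70-0.97 | 3-30% |
| Separately by treatment path | 0.83-1.00 | 0-17% |
| Within each strategy | 0.91-1.00 | 0-9% |

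At the favourable end these equal 1/0.62 = 1.61 and 1/0.91 = 1.10 times as many participants at that visit, for the first and last rows. In further runs, a pooled model with arm but no path terms had contrast variance 1.00-1.03 times that of plain complete cases, so it recovered nothing. With path indicators the ratio was 0.84-1.02, a partial recovery.

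A richer augmentation, with separate regressions in each path, lost up to 12% at correlation 0.3 with 60% unobserved. The common-slopes version was no less precise than any version of the planned weights.

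**The case against.** The strongest reply is that nothing here is wrong. Weighting complete cases is valid under missing at random when the observation model is correct, these are secondary analyses, and augmentation adds a model to prespecify with about 45 families per re-randomized path. All of that stands.

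A reader might go further and infer that the plan throws away the earlier outcomes of families cut short. The SAP does not support this: previously observed variables enter the observation model, which is fitted to those families too, and the 1-month outcomes have their own comparison.

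A reader might also attach one figure to the loss, such as 10-25%, or hold that the weights can never help a contrast because their effect cancels between strategies. Neither follows. The cancellation belongs to a pooled model without path terms, and the SAP does not say pooled. Its text speaks of means for each strategy, so a fit within strategy is at least as natural, and there augmentation adds at most about 9%. Any single band would need a share cut short and a correlation that the documents do not report. The assumed correlations are also not shown to hold for seizure outcomes or healthcare utilization, which may be binary or counts.

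These arguments shrink the gain but do not remove the case for a low-cost change that uses only data already collected.

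**Conclusion.** The point holds as an efficiency and robustness improvement to the 6- and 12-month secondary comparisons, not as an error or a source of bias. The reduction in contrast variance runs from nil to 38%, depending mainly on a choice that the SAP leaves open; if the observation model is fitted within strategy it is no more than about 9%. All of this rests on a cut-off unrelated to outcome, 20-60% unobserved, correlations of 0.3-0.7, a 1:1 second randomization and continuous outcomes. Simulation error is a few percentage points per cell. Apart from precision, augmentation gives double robustness: under missing at random the estimate stays consistent if either the observation model or the outcome regression is correct.

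**What to change.** In the SAP's Handling of Missing Data, make the augmented inverse-probability-weighted estimator the definitive analysis for each strategy mean. Prespecify a short outcome regression: treatment-path intercepts; common slopes for the baseline value, Stage 1 adherence and the latest earlier follow-up value; and a suitable link for binary and count outcomes.

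As a minimum, keep the planned weights but state that the observation model is fitted by strategy or by treatment path (control, intervention responders, continued feedback, problem-solving), with the latest earlier outcome in it.

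In the same paragraph, separate visits never scheduled because of enrolment date from dropout. If enrolment date entered the logistic model, the probability of observation would be zero after the cut-off and the weights would be undefined.

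The cost is SAP wording and programming, with no new data. The downside is one more model to prespecify, which must have few terms because each re-randomized path holds about 45.

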**Epilepsy Adherence in Children and Technology (eACT): Fostering
Medication Adherence in Children With Epilepsy Using mHealth
Technology**

Clinicaltrials.gov NCT03817229

Unique Protocol ID: 2018-8411

Version 1.0-5/20/25

Power and Sample Size Estimation

Sample size estimation was informed by results of previous studies of adherence interventions. Effect sizes for education-focused adherence interventions with reminders in other chronic conditions relative to controls (e.g., treatment as usual, pre-post) range from 0.08-0.20 [42, 43], while those with adherence feedback range from 0.78-1.03 [44, 45]. Specifically, an HIV study found that individualized adherence feedback demonstrated a large, standardized effect size (Cohen's $d=0.78$) [44]. Similar and higher effect sizes have been found for mHealth interventions that include education, automated digital reminders, or individualized feedback in adult samples including asthma, diabetes, and heart disease (Cohen's $d=0.70-2.51$) [46-48].

Given the range of observed effect sizes and taking into account the size of clinically meaningful changes in adherence, sample size was determined to detect a small-to-moderate standardized effect size (Cohen's $d=0.36$) for the primary analysis of SMART Stage 1 comparing intervention to control with 80% power with significance level 0.05. Assuming 2:1 randomization to intervention vs control yields a conservative total sample size estimate of 270, with ~180 participants randomized to intervention and ~90 to control. This sample size leads to 97% power to detect a moderate standardized effect size (Cohen's $d=0.50$).

Power for the secondary analysis involving pairwise comparison of the intervention strategies embedded in the SMART is informed by effect sizes for our face-to-face problem-solving adherence intervention, which incorporates individualized adherence feedback relative to treatment as usual. These effect sizes ranged from from 0.95 (1st problem-solving session) to 1.59 (2nd problem-solving session). Power analyses for comparison of intervention strategies require additional unknown assumptions, such as the anticipated response rate to intervention at the end of Stage 1. Assuming a 50% response rate to SMART Stage 1 intervention and a Bonferroni multiplicity adjustment, the proposed sample size provides 80% power with significance level 0.05 to detect a standardized effect size of $d=0.69$ between any pair of the embedded intervention strategies #1 - #3.

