To achieve the proposed sample size, the planned study sample was 600 participants across sites, with the goal of approximately 330 of the 600 being randomized (i.e., 10% attrition during the baseline phase, and 45% would be > 95% adherent, completing the study before randomization) [5]. Following initial randomization, these ~300 participants were to be assigned in a 2:1 ratio to intervention ($n=200$) and control ($n=100$). Making a conservative assumption of 10% attrition of participants in each initial SMART intervention arm results in anticipated $n=180$ randomized to intervention and $n=90$ randomized to control at the end of Stage 1. However, per federal and institution specific guidelines, recruitment was suspended during the COVID-19 pandemic, and the study team determined that 450 participants would need to be enrolled for $n=180$ to be randomized to the intervention arm and $n=90$ randomized to the control arm.

Statistical Analysis Plan

Primary Analysis Plan:

An intent to treat approach will be undertaken for all analyses, and a significance level of 0.05 will be used. The primary analysis examines the efficacy of the mHealth adherence intervention in caregivers of youth (ages 2-12) with newly diagnosed epilepsy (< 2 years) on electronically monitored adherence relative to control on the basis of the primary outcome of change in electronically monitored adherence from baseline, calculated using the baseline and final 30-day adherence. The primary hypothesis is that participants initially randomized to intervention will exhibit significantly greater improvements in adherence compared to those randomized to control from baseline to end of Stage 1. Although sample size was calculated conservatively based on use of a two-sided, two-sample t -test with unequal sample sizes, to achieve a more efficient analysis with enhanced power, the primary analysis will be based on a standard analysis of covariance with adherence at the end of Stage 1 as the dependent variable and baseline adherence as the covariate.

Secondary Analysis Plan:

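### Must the SAP say how participants never scheduled for the 6- or 12-month visit count in its 10% missingness rule and its weights?

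*SAP*

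**What the plan says.** The Secondary Analysis Plan of the SAP promises comparisons of all three strategies on adherence, seizures, quality of life and "healthcare utilization at 1-, 6-, and 12-months post-intervention". Handling of Missing Data then sets one rule for all of these. "Stage 2 and later outcomes will be assumed to be missing according to a MAR mechanism". Complete cases are analysed "If the extent of missingness is less than 10% for each strategy". Weighted complete cases serve as a sensitivity analysis, and also "to obtain a definitive analysis if the extent of missingness is greater than 10" per cent. The weight is "the reciprocal of the estimated probability not dropping out of the study/having the outcome observed as a function of baseline and previously observed variables". The Primary Analysis Plan adds that "An intent to treat approach will be undertaken for all analyses".

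The protocol fixes who has a late visit. Under Section 5 and the footnotes to the measures table in Section 8, 6-month questionnaires are for those enrolled before 3/8/2023 and 12-month questionnaires for those enrolled before 12/9/2022. The SAP does not mention these cuts. It does record a different pandemic effect, that "the study team determined that 450 participants would need to be enrolled".

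**The concern.** A participant enrolled after a cut-off did not drop out, yet has no outcome. That person passes the part of the weighting phrase before the slash and fails the part after it. The 10% rule has no stated denominator, so an administrative cut could by itself move a comparison from complete-case to weighted analysis. The SAP is marked "Version 1.0-5/20/25", after both cuts and after the last scheduled visit, so the facts were available when it was written.

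The possible cost is threefold: the definitive result could be chosen after both are known; a weighting model fitted to everyone could model calendar time instead of dropout and give unstable weights; and readers might not know which population the late results describe. Up to 24 comparisons are involved (4 outcome groups × 3 pairs × 2 times). That is an upper bound, because Section 8 of the protocol has chart review covering the whole study period, so outcomes taken from charts may not be cut.

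**Working it through.** **The plan's own figures.** With 180 and 90 participants and two-sided 0.05, power is Φ(d/√(1/180+1/90) − 1.96). At d=0.36 this is Φ(2.79 − 1.96) = 79.6%, and at d=0.50 it is Φ(3.87 − 1.96) = 97.2%, against 80% and 97% stated. For the strategy comparison, 45 per group (180 × 50% non-responders, split 1:1, an assumption) and alpha 0.05/3 give Φ(0.69/√(2/45) − 2.39) = 81.0%, or 79.5% by the noncentral t, against 80% stated. All reproduce, so 270 is a fair base for what follows.

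**Dates.** 12/9/2022 plus 20 months is 8/9/2024, which is 284 days before 5/20/25. 3/8/2023 plus 14 months is 5/8/2024. The two cuts are 89 days apart.

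**The 10% limit.** Let u be the share never scheduled and d the dropout among those scheduled. On an all-randomized count, missingness is 1 − (1−u)(1−d). On a scheduled-only count it is d. At d=5%:

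- u=8%: 1 − 0.92×0.95 = 12.6%
- u=20%: 1 − 0.80×0.95 = 24%
- u=33%: 1 − 0.67×0.95 = 36%

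The limit is reached at u = 1 − 0.90/0.95 = 5.3%, or 14 of 270. At d=8% it is reached at u = 1 − 0.90/0.92 = 2.2%, or 6 of 270. The count can therefore decide the label.

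The documents do not give u. At a constant 450 over 36 to 60 months (assumed), 89 days is 2.9 months, or 5% to 8% of enrolment. The SAP says recruitment was suspended, so constant accrual is only a rough guide.

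**What the label changes.** Never-scheduled participants supply no outcome, so complete-case analysis uses the same outcome records on either count. Weighting is carried out both below and above 10%. The open items are which result is called definitive and which records fit the weights.

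**Size of the difference.** Simulation settings: 270 participants (180/90), about 50% response, 1:1 re-randomization (assumed), true #3 minus #1 of 0.36, 4.7% missing among scheduled participants, 2,000 runs. Weights come from logistic regression on treatment history, response, a baseline variable, the 1-month outcome and a variable with correlation r to enrolment date. The average contrast is 0.35 to 0.36 on every reading.

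| Late-enrolled share (assumed) | 8% | 20% | 33% |
|---|---|---|---|
| Variance ratio, pooled/scheduled-only, r=0 | 0.99 | 1.00 | 0.99 |
| r=0.5 | 1.02 | 1.05 | 1.19 |
| r=0.8 | 1.01 | 1.28 | 1.82 |
| Significance differs (scheduled complete-case vs pooled weighting), r=0 | 2.7% | 3.7% | 3.8% |
| r=0.5 | 3.6% | 7.3% | 12.8% |
| r=0.8 | 5.3% | 14.0% | 21.0% |

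A similar simulation (1,500 runs) at r=0.2 to 0.3 gives variance ratios of 1.00, 1.01 and 1.00 to 1.04. It also shows complete-case and weighted results disagreeing in about 2% of trials within the same scheduled set, so most of the r=0 disagreement is ordinary difference between estimators.

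The ordering can also reverse. With sequential weights that use the 6-month outcome, about 12% outcome-related dropout, 25% late and no date-linked variable, pooled weighting has SD 0.161 against 0.173, a variance ratio of (0.161/0.173)² = 0.87.

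**The case for a change.** The strongest case for a change is that the threshold is low, the cuts were known, and the remedy is one filter on enrolment date plus a few sentences. Late enrollees have zero chance of a late visit, which a dropout model cannot represent. The COVID-19 impact measure is collected at baseline and every later questionnaire visit and could track enrolment date. At r=0.8, a comparison with 80% power under scheduled-only weighting would have 79%, 70% or 55% under pooled weighting at the three assumed shares.

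The omission stands, and so does the arithmetic of the limit. The harm is not shown. The SAP names no weighting variables, and no document makes the COVID-19 measure one or gives its correlation with enrolment date. The intent-to-treat sentence and the words after the slash lean towards counting all randomized participants, though they do not settle it. On that reading the assumption needed is that enrolment date is unrelated to outcome given the modelled variables. For a calendar cut this is what missing at random means, and the SAP assumes it.

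Restricting to scheduled participants is also not plainly better. It narrows the conclusions to earlier enrollees and can cost precision. The documents' differing treatment of enrolment on exactly 3/8/2023 is a clerical matter of one day.

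**Conclusion.** No change to the plan is called for. The SAP leaves a definition unwritten that an analyst holding the protocol's enrolment cut-offs can fill sensibly. That means separating visits never scheduled from dropout, showing the number scheduled per strategy, and not letting enrolment date drive a dropout model. Choosing between all randomized and scheduled participants is a fair trade-off between target population and precision, and either is defensible if reported.

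No bias appears on either reading. The variance ratio is 0.99 to 1.00 when no weighting variable tracks enrolment date, and at most 1.04 at correlations of 0.2 to 0.3. It reaches 1.82 only with a correlation of 0.8 and a third of participants enrolled late, and the documents establish neither. The conclusion rests on the SAP's missing-at-random assumption and on no weighting variable being strongly tied to enrolment date. It concerns secondary comparisons at 6 and 12 months only.
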